5.5. Participant Adherence Monitoring

Study drug containers will be returned to site investigators at the conclusion of each 2-week period during dose escalation (weeks 2, 4 and 6), and at the Week 12, 24 and 36 visits. Pill counts will be performed to assess participant adherence with prescribed study medication.

5.6. Concomitant Therapy

Medication use (both oral and intravenous) will be collected at baseline and throughout the course of the study. Digoxin use, dual ACE inhibitor/ARB therapy and non-selective beta blocker use are exclusion criteria. If these medications are initiated during follow-up the treating clinician will be contacted by the research team. For digoxin or dual ACEI/ARB use, if the prohibited drug cannot be discontinued, study medication will be withdrawn and participants will continue to be followed. For non-selective beta blocker use, it is anticipated that the treating clinician will be comfortable substituting a selective beta blocker but if not, study drug will be discontinued and the participant will continue to be followed.

5.7. Packaging

Study drug will be distributed in patient-specific containers with 17 capsules for every 2-week period during the dose escalation phase, 49 capsules for the weeks 6-12, and 91 capsules for weeks 12-24 and weeks 24-36. The extra capsules allow for continued dosing in the event of a short delay in dispensing the subsequent study drug supply. Labeling will include patient name, patient ID, protocol number, study-center, expiration date, and prescribing physician (study investigator).

5.8. Blinding of Study Drug

Generic SPL will be purchased, and matching placebos will be prepared by the University of Pennsylvania IDS. The IDS will send study drug to the Clinical Center research pharmacies and the identity SPL and matched placebo will be concealed from both investigators and participants. Only the IDS and the database programmer will be unblinded. See **Section 8.5** for information on unblinding procedures, if needed.

5.9. Receiving, Storing, Dispensing and Returning Study Drug

5.9.1. Receiving Study Drug Supplies

The University of Pennsylvania IDS will ship study drug to the Clinical Center research pharmacies and will maintain inventory at the pharmacies based on study drug utilization. Each Clinical Center research pharmacy will be responsible for maintaining detailed records regarding the receipt of study drug. General Study Product Accountability, Patient Specific Study Product Accountability, and if necessary, Shipment Tracking Accountability Logs will be maintained by the site pharmacist to document study drug use. Documentation includes study product receipt, storage, dispensing, and final disposition. Study product will be inventoried at least once per month within 30 days of the count for the previous month.

5.9.2. Study Drug Storage

SPL and matched placebo will be stored at <25°C. Study supplies will be stored in the central IDS pharmacy at the University of Pennsylvania until shipment to the Clinical Center research pharmacy. Study drug will be stored at the Clinical Center's research pharmacy until distribution to the participant.

5.9.3. Dispensing Study Drug

The Clinical Center pharmacist or trained site designee will dispense study drug to the participant and complete a dispensing/accountability log for each participant. Designated site personnel with responsibility for dispensing and reconciling study drug will have appropriate training and documentation of this training will be maintained in the site's regulatory binder.

5.9.4. Return or Destruction of Study Drug

Study drug containers will be returned by participants at the end of each 2-week, 6-week, or 12-week period and remaining pills will be counted to assess adherence. Unused supplies of study drug will be destroyed by the Clinical Center research pharmacy once the pill count is completed and documented. In the event that a participant does not return study drug containers he/she will be instructed to stop taking any study drug from the non-returned container.

6. Study Procedures

A schedule of study visits and procedures is provided in the Study Procedures Table in **Section 15.1** (Attachments).

6.1. Pre-screening Activities

Dialysis unit records and study center medical records will be reviewed by Clinical Center study personnel to assess eligibility. The treating nephrologist for a potentially eligible patient will be contacted to further assess eligibility and obtain permission to contact the patient. Patients remaining eligible after these procedures will be approached in person at the dialysis unit to confirm eligibility for and interest in participation. Participants signing IRB-approved informational flyers that indicate willingness to be called by study personnel may be pre-screened by telephone.

6.2. Screening Visit (Day –30 to Day 0)

Potential participants expressing interest in enrolling in the study will be scheduled for a Screening visit. This visit may take place at the local dialysis unit or at the Clinical Center and may take place over more than 1 visit. Screening activities must be completed within 30 days prior to the baseline visit.

Informed consent will be obtained and documented before any study procedures are performed. Demographic data (age, sex, race), medical history (hypertension, coronary artery disease, coronary revascularization, diabetes, hypercholesterolemia, cerebral or peripheral vascular disease, peptic ulcer disease, cancer, smoking, arrhythmia, cause of ESRD, dialysis vintage,

prior transplant), dialysis unit labs (chemistries, intact parathyroid hormone, complete blood count), and dialysis prescription will be collected during Screening. Blood will be drawn for serum pregnancy testing in women of childbearing potential. Participants will perform an inter-dialytic urine collection prior to or within seven days following the baseline visit, for assessment of residual renal function. The urine collection will begin immediately after dialysis and continue until the start of the next dialysis session, and will be performed during one of the 44-hour (approximately) inter-dialytic periods rather than during the 68-hour (approximately) inter-dialytic period.

Potential participants will be excluded if there is any serum potassium value of ≥ 6.5 mEq/L within 3 months prior to the Baseline/Randomization visit or if there is any serum potassium value ≥ 6 mEq/L within 2 weeks prior to the Baseline/Randomization visit. It is required that there be at least one serum potassium value obtained within 2 weeks prior to Baseline. The potassium measurement can be obtained either through routine clinical testing or as a research test. Participants who do not meet eligibility can be rescreened one additional time.

If the participant has agreed to participate in the heart rhythm monitoring sub-study, the first monitoring will be performed between the screening and baseline/randomization visits. The participant will wear the Medtronic SEEQ heart monitor for 7 consecutive days. Participants will receive the monitor kit from the research team and will return the kit after the monitoring period.

The heart rhythm data will be transmitted in batches to the DCC and will not be analyzed until a participant has completed participation in the study. Reports will not be generated for clinical use by the investigators, treating physicians, or participants. Participants will be informed of this at the time of enrollment and will be instructed to report to the research team or their treating physician any concerning symptoms they have while wearing the heart rhythm monitor. The same approach will be used for heart rhythm monitoring that takes place at 6 weeks and 32-36 weeks.

6.3. Baseline/Randomization Visit (Day 0)

The Baseline/Randomization visit will take place on a non-dialysis day during the short (approximately 44-hour) inter-dialytic interval. At this visit, medication use, vital signs, a brief physical examination and adverse events will be recorded, and eligibility will be confirmed. Once eligibility has been confirmed, randomization to treatment group will be performed through the centralized Data Management System.

Serum and plasma will be collected, aliquoted, and shipped for batched measurement of cardiac and inflammatory markers and for long-term storage. Whole blood will be collected for DNA extraction. Blood will also be drawn for local measurement of chemistries and complete blood count. If blood cannot be collected on the day of the Baseline/Randomization visit (Day 0), it should be collected the following day prior to the dialysis session and before the initiation of study drug. If blood for batched analyses, long-term storage, and DNA extraction cannot be obtained on the day of randomization or the following day, it is acceptable to obtain the blood within the 10 days prior to the Baseline/Randomization visit, and, if on a dialysis day, prior to initiation of the dialysis session. However, the blood for local measurement of chemistries and

complete blood count will be obtained on the day of or the day after the Baseline/Randomization visit rather than within 10 days prior.

Tissue Doppler Index echocardiography (TDI echo) will be performed on the day of the Baseline/Randomization visit. If the TDI echo cannot be performed at that visit (Day 0), it should be completed as soon as possible thereafter and within 7 days after the Baseline/Randomization visit. The echo must be performed on a non-dialysis day during the short (approximately 44 hour) inter-dialytic interval. A subset of participants will have positron emission tomography (PET scan) (after exclusion of pregnancy).

A 2-week supply of study drug will be dispensed and the participant will be instructed to start the study drug the following day, after dialysis.

6.4. Week 1, Week 2, Week 3, Week 4, Week 5, and Week 6 Visits (window for each: -4 to +3 days)

Blood will be obtained for measurement of serum potassium at 3-5 days and 2 weeks after the initiation of each new study drug kit during the dose escalation phase. Participants will be interviewed weekly in person or by telephone for the occurrence of serious adverse events and adverse events of interest. Adverse events of interest include hypotension, gastrointestinal symptoms, gynecomastia/breast tenderness, hyperkalemia and rash (see **Section 8.3.1**). Dialysis unit records will be reviewed for inter-current laboratory values, the occurrence of hypotension, and changes to the dialysis prescription. The dose of study drug may be reduced if a participant experiences dose-limiting adverse events, as outlined in **Section 6.8 and 6.9**.

A new supply of study drug will be dispensed and used pill containers returned at the week 2, week 4, and week 6 visits as described in sections **5.9.3 and 5.9.4**. Pill counts will be performed to assess participant adherence with study medication, and unused study drug will be destroyed by the Clinical Center research pharmacies once the pill count has been documented.

At the end of the dose escalation phase, participants in the heart rhythm monitoring sub-study will undergo heart rhythm monitoring using the Medtronic SEEQ device. The participant will wear the Medtronic SEEQ heart monitor for 7 consecutive days. Participants will receive the monitor kit from the research team and will return the kit after the monitoring period.

6.5. Week 8 (-4 to +3 days), Week 12, Week 16, Week 20, Week 24, Week 28, and Week 32 Visits (-7 to +7 days for all except Week 8)

Participants will be contacted at weeks 8, 12, 16, 20, 24, 28 and 32 either in person or by telephone to review the occurrence of serious adverse events and adverse events of interest as described in **Section 6.4**. Dialysis unit records will be reviewed for inter-current laboratory values, the occurrence of hypotension, and changes to the dialysis prescription. If a serum potassium value is not available in the participant's dialysis unit record, corresponding to the date of the monthly study visit (plus window), blood will be obtained from the participant for measurement of serum potassium. The dose of study drug will be reduced for participants experiencing dose-limiting adverse events as outlined in **Sections 6.8 and 6.9**.

New study drug will be dispensed and used pill containers returned at the week 12 and week 24 visits as described in **Sections 5.9.3 and 5.9.4**. Pill counts will be performed to assess participant adherence with study medication, and unused study drug will be destroyed once the pill count has been documented.

Participants in the heart rhythm monitoring sub-study will undergo heart rhythm monitoring using the Medtronic SEEQ device for a continuous 7 day period between Weeks 32 and 36. Participants will receive the monitor kit from the research team and will return the kit after the monitoring period.

6.6. Week 36 Visit (End of Treatment) (-7 to +7 days)

At the Week 36 visit, participants will be interviewed in person to review the occurrence of adverse events as described in **Section 6.4**. Dialysis unit records will be reviewed for inter-current laboratory values, the occurrence of hypotension, and changes to the dialysis prescription. Pill containers will be returned and unused pills counted and destroyed. Serum and plasma will be collected, aliquoted, and shipped for batched measurement of cardiac and inflammatory markers and for long-term storage. Blood will also be drawn for local measurement of chemistries, complete blood count and, for women of childbearing potential, serum pregnancy testing. If the blood collection is performed on a dialysis day, the collection should take place prior to the dialysis session. End-of- study TDI echo will be performed and a subset of participants will have a PET scan performed (following exclusion of pregnancy).

6.6.1. Early Withdrawal Visit

If a patient withdraws from the trial before the Week 36 milestone or if it becomes known that a participant will not be available for an in-person visit at Week 36 (e.g., due to relocation), an Early Withdrawal visit will be scheduled to conduct the final comprehensive assessments that otherwise would be performed at Week 36. For participants in the heart rhythm monitoring sub-study, the assessments will include heart rhythm monitoring using the Medtronic SEEQ device for 7 continuous days at the time of early withdrawal, if possible. Patients who stop taking study medication are not considered early withdrawals and will be asked to continue to provide follow-up data on the study schedule and to participate in the final comprehensive assessment at Week 36.

6.7. Week 40 Visit (-7 to +7 days)

At the Week 40 visit (4 weeks after end of treatment), patients will be interviewed in person or by telephone to review the occurrence of adverse events as described in **Section 6.4**. Dialysis unit records will be reviewed for inter-current laboratory values, the occurrence of hypotension, and changes to the dialysis prescription.

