3.1. General Design

This is a randomized, placebo-controlled 4-arm trial that will compare placebo with 3 doses of SPL. Participants will be randomized in a 2:1:1:1 fashion to placebo or SPL, with equal proportions randomized to each of 3 SPL doses: 12.5, 25 or 50 mg once daily. As shown in **Figure 1**, the study will be conducted in 2 phases – a dose escalation phase and a treatment phase.

All participants randomized to SPL will initiate treatment at 12.5 mg daily. Participants will be evaluated weekly for tolerability, hypotension and hyperkalemia. At 2 weeks, if the initial dose has been tolerated, participants randomized to the 25 or 50 mg SPL arm will increase the dose to 25 mg for 2 weeks with weekly evaluation for tolerability, hypotension and hyperkalemia. Participants randomized to 12.5 mg SPL or placebo arm will continue on the same dose with weekly evaluation for tolerability, hypotension and hyperkalemia.

[figure not shown]
At 4 weeks, participants randomized to the 50 mg SPL arm will increase the dose to 50 mg if the 25 mg dose was tolerated with weekly evaluations for tolerability, hypotension and hyperkalemia.

until 6 weeks. Participants randomized to 12.5 mg, 25 mg, or placebo will continue on the same dose with weekly evaluation for tolerability, hypotension and hyperkalemia until 6 weeks.

In order to maintain the blind, during the dose escalation phase all study participants, regardless of randomized assignment, will receive new study drug kits every 2 weeks and will be evaluated weekly.

At the end of the dose escalation phase, participants will continue treatment based on the randomized dose assignment for an additional 30 weeks (treatment phase) such that the total duration of study medication is 36 weeks. As described in **Sections 6.8 and 6.9**, the dose of SPL or placebo will be decreased during the dose-escalation and follow-up phases for hypotension, hyperkalemia or other dose limiting side-effects.

Figure 1. Study Design

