8.2. Adverse Event Tracking Period

The study period during which adverse events must be tracked and reported is normally defined as the period from the initiation of study procedures to the end of the study treatment follow-up. For this study, the study treatment follow-up is 4 weeks following the last dose of study drug.

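### The Week 40 window lets the last scheduled safety contact fall up to 7 days before the 4-week adverse event tracking period in Section 8.2 ends

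*Combined protocol and SAP*

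**What the plan says.** Section 8.2 defines the period in which adverse events must be tracked and reported, and fixes its end: "For this study, the study treatment follow-up is 4 weeks following the last dose of study drug".

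Section 6.7 supplies the contact that serves this period: "At the Week 40 visit (4 weeks after end of treatment), patients will be interviewed in person or by telephone". At that contact adverse events are reviewed, and dialysis unit records are checked for laboratory values, hypotension and prescription changes. The visit carries a two-sided window, "Week 40 Visit (-7 to +7 days". In table 15.1 the only column after Week 40 is for as-needed contacts.

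The end-of-treatment visit has a window of its own: "Week 36 Visit (End of Treatment) (-7 to +7 days". Section 3.1 sets the length of treatment, "such that the total duration of study medication is 36 weeks", and Section 5.7 sets the supply, "91 capsules for weeks 12-24 and weeks 24-36".

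The plan does not say whether the Week 40 window is counted from Day 0 or from the actual end of treatment. It also does not say when dosing stops if the Week 36 visit is late.

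**The concern.** The tracking period and the final contact have the same nominal length of 4 weeks. Any contact made on the early side of the window therefore falls before the period has ended. Such a contact is within window, so it would not be flagged as a deviation, and no later contact is scheduled.

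What is at stake is complete capture of post-treatment safety events. Safety is the stated focus of this pilot, and its primary safety endpoints are potassium above 6.5 mEq/L and serious hypotension. Week 40 is the only scheduled post-treatment review of the dialysis records in which such events would be found. After it, Section 8.2.1 relies mainly on events that the participant or the personal physician believes to be related, and Section 8.4 adds possibly related SAEs after the study period. Section 8.1.1, by contrast, defines an adverse event regardless of relatedness, and 8.2 adds no such condition.

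**Working it through.** **Inputs**
- Week 36 = 36 × 7 = Day 252, window ±7 days: Days 245 to 259 (Section 6.6).
- Week 40 = 40 × 7 = Day 280, window ±7 days: Days 273 to 287 (Section 6.7).
- Tracking period: 28 days after the last dose (Section 8.2).
- Treatment duration: 36 weeks, to about Day 252 (Section 3.1).
- Last kit: 91 capsules for 12 × 7 = 84 days, so 7 spare (Section 5.7).

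**The plan's own figure.** 280 - 252 = 28 days. This reproduces the stated 4 weeks, so the nominal schedule is consistent and only the windows need checking.

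**Gap from last dose to final contact, under each reading**

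| Reading | Shortest gap | Longest gap | Most uncovered |
|---|---|---|---|
| Week 40 counted from actual end of treatment, as 6.7 describes it | 28 - 7 = 21 | 28 + 7 = 35 | 7/28 = 25% |
| Last dose on Day 252, Week 40 window from Day 0 | 273 - 252 = 21 | 287 - 252 = 35 | 7/28 = 25% |
| Both windows from Day 0, dosing to the actual Week 36 visit | 273 - 259 = 14 | 287 - 245 = 42 | 14/28 = 50% |

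No reading gives a shortest gap of 28 days.

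**How far the third reading carries.** A kit dispensed on Day 168 lasts to 168 + 91 = Day 259, so the supply would allow dosing to a late Week 36 visit. Each window has 15 days, giving 15 × 15 = 225 permitted day pairs. The gap is below 28 days in 105 of them (46.7%), below 21 days in 28 (12.4%), and exactly 14 days in 1 (0.4%). These are counts of permitted combinations, not probabilities.

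**Who is affected.** With the Week 40 window counted from Day 0, the earliest compliant contact is Day 273. A shortfall then needs a last dose after Day 273 - 28 = Day 245. Participants who stop drug earlier stay on the visit schedule (Sections 4.4.2 and 6.6.1), so their last scheduled contact is at least 28 days after their last dose.

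**The case against.** The strongest reply is that this is ordinary visit-window tolerance around a schedule that is nominally right, and that an early call does not end the duty in 8.2. Within the 28 days that duty covers all tracked events, and SAEs known to the site go to the coordinating center within 24 hours (8.4). Section 8.2.1 also requires follow-up of unresolved events, and notification of any later death or adverse event that may reasonably be related. This stands as far as it goes: reporting continues, and what is missing is a scheduled contact. It does not remove the mismatch, because an event that nobody asks about, and that nobody thinks related, may never reach the site.

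A reader might infer more than the documents support, in three ways.

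- **Half the period is uncovered.** The 14-day gap needs both windows counted from Day 0 and dosing carried to Day 259. Section 6.7 describes Week 40 as 4 weeks after end of treatment, and Section 3.1 sets 36 weeks of medication in total. The spare capsules are there to cover a delay in dispensing the next supply, and no supply follows Week 36. The protocol's silence on the anchor leaves this reading open, but as a worst case only.
- **Nearly half of participants are affected.** The 46.7% would be a share of participants only if visit days were spread evenly over the windows. Nothing in the documents supports that assumption.
- **The safety comparison is distorted.** Section 7 specifies no separate post-treatment event percentage, and the windows are the same in all blinded, randomized arms. No bias between arms is shown.

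**Conclusion.** The mismatch is real and minor. On every reading, a compliant final contact can precede the end of the tracking period in 8.2. The supported size is up to 7 of 28 days without a scheduled contact, for participants treated to about Week 36. This rests on the Week 40 window being counted from the end of treatment, or on the last dose falling at 36 weeks. A shortfall of up to 14 days is possible only under the two further conditions in the third reading, and it should not be quoted as the size of the problem.

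The consequence is limited to active ascertainment at the end of post-treatment safety follow-up. Sample size, power, the Week 36 efficacy endpoint and the between-arm comparisons are not shown to be affected. How many participants would be contacted early cannot be derived from the documents.

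**What to change.** In Section 6.7 and table 15.1, state the date from which the Week 40 window is counted. Hold the final interview and record review no earlier than the later of (a) scheduled Week 40 and (b) 28 days after the last dose, with a one-sided window, for example 0 to +7 days.

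- Last dose on Day 252: both dates are Day 280, so the contact falls on Days 280 to 287 and the gap is 28 to 35 days.
- Last dose on Day 259: the later date is 259 + 28 = Day 287, so the contact falls on Days 287 to 294 and the gap is again 28 to 35 days.
- Last dose at Week 10 (Day 70): 70 + 28 = Day 98 is earlier than Day 280, so Week 40 governs and the participant stays on the full schedule.

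The third case is why the contact should not be counted from the last dose alone: that would pull it forward to about Week 14 for someone whom Sections 4.4.2 and 6.6.1 keep in follow-up.

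The alternative is to leave the window as it is and restate 8.2 as the period the schedule covers.

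The cost is a few words in 6.7 and 15.1. The earliest permitted contact moves from Day 273 to Day 280, or to Day 287 after a last dose on Day 259, so some final calls come one to two weeks later. Section 6.7 already allows the interview by telephone.
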